Aim1: We will evaluate change in postural control over 16 sessions of Tango (exp) vs HEX (control) (n=26 per group; 1:1 randomization) as primary endpoint. As secondary measures, we will assess: balance function (i.e., TUG) and PROs (i.e., symptoms, pain, fatigue, mood, quality of life) *monthly* including 1 month post-intervention completion; postural control and symptoms *within-session*; and falls incidence *weekly for 6 months following intervention completion*. **Hypothesis:** At primary endpoint, members of the exp group will show more improvement than members of the control group in measures sensitive to neuropathy disease state (i.e., sway variability and area).

a. Primary measure: Posture (RMSml): has shown clinically relevant for future fall prediction[40–43] and neuropathy detection in cancer[44–46] and diabetes[47,48] in a host of studies. As our primary measure we will calculate this measure of medial-lateral sway variability (RMSml). Postural control (30 s duration) will be collected 2x/week during multiple baseline testing, monthly thereafter for HEX, and before and after each session for the Tango group. Center of pressure (COP) data will be recorded (1000 Hz) as participants stand quietly on a level, static balance platform (Bertec Corp, Columbus, OH) with eyes closed (QEC). As in past work[20,38,44–46], we will collect 30 second (s) of COP data and interpret these data with regard to healthy within-subject variability as defined in a middle-aged cohort [20].

RMSml will be calculated (as described by Prieto[49]) as the root-mean-squared value of COP excursion in the medial-lateral direction (mm), a formula which effectively returns the standard deviation from the mean. All data will be captured using custom software written in LabView (National Instruments, Austin, TX, US). Our team ([name], [name]) has pioneered the biomechanical assessment of balance deficits associated with cancer treatment and neurorehabilitation [20,38,44–46]. Using center-of-pressure (COP) measures captured with portable force platform equipment, we have quantified the balance dysfunction that accumulates with cancer treatment sessions (Fig 1) [1,46,50] and identified a potential effect of Tango to remediate these effects[38]. Finally, in order to translate this quantified measurement paradigm to clinical care of individuals, we published normative measures of within-subject variability (WSV) [20] to enhance our interpretation of treatment effects.

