Feedback is used to improve future sessions. Monthly, we prompt participants to rate the likelihood of future engagement. **The Intrinsic Motivation Inventory (IMI)** was developed from the perspective of Self Determination Theory to assess 7 dimensions of experience: Interest/Enjoyment, Perceived Competence, Effort/Importance, Pressure/Tension, and Choice[39,57–61]. We administer the 9 item short form of the IMI weekly to optimize instruction around high Perceived Competence and low Pressure/Tension[58,59] as well as explore relationships between adherence, motor effects, and IMI dimensions (including perceived benefit (Effort/Importance)). The Patient-Reported Outcome version of the **Common Terminology Criteria for Adverse Events v5 (PRO-CTCAE):** developed by NCI, is standard protocol in oncology to screen for signs of depression, anxiety, and apathy associated with cancer treatment or progression[62]. While not an outcome measure, we collect this staff-administered assessment per visit for adverse event screening, using the data to monitor and compare descriptive

statistics between groups. Changes in depression, anxiety, or apathy identified within check-ins, will be addressed.

c. *Within-Session Effects* Posture: will be captured before and after each Tango session in order to assess within-session change over time. A subset of **PROs**: (i.e., CIPN-20, BPI, and CRF) will be collected routinely before and after Tango training to allow analysis of within-session change. Finally, satisfaction with intervention will be collected after each session

Aim2: We will evaluate change in gait variability after 16 sessions of Tango (exp) vs HEX (control) (n=26 per group; 1:1 randomization). As secondary measures, we will analyze local and orbital dynamic stability (pre, post, and 1mo post-intervention), PROs (monthly), and falls incidence (weekly) following intervention completion. **Hypothesis:** At primary endpoint, members of the exp group will improve more relative to control group members in gait variability (i.e., stride-to-stride variability in speed).

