
Data collection: data may be collected using paper or electronic (e.g. MyCAP) versions of approved instruments.

Data storage: paper versions of source documentation will be kept in a locked cabinet within an OSU office that is accessible only to OSU clinical or research staff. Electronic data may be stored in a password protected spreadsheet or through RedCAP.

Interventions: training may be delivered in-person, via video conferencing, or via asynchronous instruction.

E. Internal Validity

All measures will be conducted by a researcher trained in the administration of the measure.

F. Data Analysis

Sample Size Justification: Preliminary data from our group was used to determine sample size requirements for this proposed randomized trial. **Aim 1:** Five cancer survivors with postural control deficits (RMSml>4.0mm) at baseline who participated in Tango practice improved RMSml from mean(SD) of 7.9(1.2) at baseline to 4.6(0.5) after 8 Tango sessions. Assuming more heterogeneity in our analysis sample, (SD=2.7 in control and intervention groups) we estimate Cohen's $d=1.22$. Thus we require an analysis sample of $n=14$ participants per group to provide 85% power at a 5% type I error rate. To account for anticipated drop-out and Aim2 analysis we will **enroll n=26 participants per group.** **Aim 2:** Preliminary data shows an Coefficient of Variation gait speed (CVspeed) SD of approximately 1.2 among survivors with neuropathy and postural deficits prior to Tango practice. With a sample size of $n=19$ per group (per Aim1) and this SD, we have 80% power to detect a difference of 1.32 ($d=1.1$). A cohort of 7 survivors with heterogeneous treatment progress (during and after chemotherapy exposure), not screened for or limited to those with postural control deficits, demonstrated a decrease in CVspeed ($p=0.003$) from 3.0(1.15) to 2.2(1.10) after ≤ 16 sessions of Tango practice ($d=0.711$). We will enroll **n=26 participants per group** to detect a reduction of this magnitude with 80% power.

Statistical Analysis Plan: Unless otherwise noted, all analyses will be performed on an intent-to-treat basis, and all hypothesis tests will be two-sided and at the 5% significance level. Enrolled participant characteristics will be summarized by assigned treatment groups.

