For **Aim 1**, a linear mixed effects model will be used to model postural sway (RMSml). Fixed effects will be included for time, treatment, treatment-by-time interactions, and concurrent medication use. Random effects for subjects will be used to account for correlation between observations from the same subject. The primary estimand will be a difference-in-difference representing the difference in mean RMSml change from baseline to week 16 between treatment groups. While we expect balance between the two groups due to randomization, we will adjust for potential confounders including baseline RMSml, age, body mass index, concurrent medications (e.g., duloxetine) and other variables if imbalance between groups occurs by chance. Similar analyses will be performed for the PROs sensory symptoms (CIPN-20), pain (BPI-SF), fatigue (0–10 Likert), quality of life (SF-36), and falls incidence following intervention completion. Finally, Pearson's R will be calculated to correlate postural control and balance outcomes, PROs, and future falls incidence.

For **Aim 2**, a similar analysis strategy will be used to compare biomechanical mobility between the two groups (linear mixed models; one-sided hypothesis test) as well as the correlation between biomechanical mobility outcomes, PROs, and falls incidence following intervention completion (Pearson's R).

Not all enrolled subjects will complete the intervention and have follow-up data. The linear mixed model analyses can use available data from all participants with at least one observation, regardless of whether or not they complete follow-up. We will compare the baseline characteristics of subjects who complete the study to those who drop out to assess the potential for attrition bias. A sensitivity analysis will be performed using multiple imputation to assess the impact drop-out has on study conclusions.

V. Funding

This project was funded, initially in Phase 1, through a 2015-16 Pelotonia Undergraduate Fellowship. We secured Phase 2 funding in 1R21AG068831 through the NIH National Institute of Aging (Note: this includes visit reimbursement for cancer survivors only).

VI. References

- [1] S.M. Monfort, X. Pan, R. Patrick, J. Singaravelu, C.L. Loprinzi, M.B. [name], A.M.W. Chaudhari, Natural history of postural instability in breast cancer patients treated with taxane-based chemotherapy: A pilot study, *Gait and Posture*. (2016). <https://doi.org/10.1016/j.gaitpost.2016.06.011>.

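### The Aim 2 gait comparison is tested one-sided, by default at 5%, without a stated reason, which is a looser standard for Tango benefit than the two-sided 5% used for Aim 1

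*Combined protocol and SAP*

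**What the plan says.** All of this is in section IV.F, Data Analysis, unless noted.

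- **Default.** The Statistical Analysis Plan states that "all hypothesis tests will be two-sided and at the 5% significance level". The same sentence opens by allowing exceptions: "Unless otherwise noted, all analyses will be performed on an intent-to-treat basis".
- **Exception.** The Aim 2 paragraph compares biomechanical mobility between groups with "linear mixed models; one-sided hypothesis test". No significance level and no rationale accompany it.
- **Hypotheses (section IV.D).** Both aims predict the same direction. Aim 1: "members of the exp group will show more improvement than members of the control group". Aim 2: "members of the exp group will improve more relative to control group members in gait variability". Only Aim 2 is made one-sided.
- **Comparator.** Section IV.A describes the second arm as an active control. Section IV.D identifies it as home exercise (HEX).
- **Aim 2 sample size.** Pilot CV of gait speed went "from 3.0(1.15) to 2.2(1.10) after" Tango practice, quoted as d=0.711, and 26 per group are to be enrolled "to detect a reduction of this magnitude with 80% power". A second statement gives 80% power at 19 per group for a difference of 1.32 with SD 1.2 (d=1.1). Neither statement says whether the test is one- or two-sided.

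**The concern.** A one-sided test at 5% puts the whole error allowance on the side of Tango benefit. A gait result favouring Tango with a two-sided p-value between 0.05 and 0.10 would count as positive under Aim 2, although the same strength of evidence would not count under Aim 1.

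The test also has no rejection region in the other direction. With an exercise comparator, a result favouring HEX is a real possibility, and this test could not declare it significant however large it was.

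The direction of the hypothesis does not explain the difference between the aims, because both hypotheses point the same way.

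**Working it through.** **1. Error rate.** With no true difference:

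| Rule | P(declare Tango better) | P(declare HEX better) | Critical t, 50 df |
|---|---|---|---|
| Two-sided 5% (plan default) | 0.05/2 = 2.5% | 2.5% | 2.01 |
| One-sided 5% (Aim 2) | 5% | 0% | 1.68 |

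The degrees of freedom are 2×26 − 2 = 50. The total type I error is 5% under both rules. What doubles is the error in the benefit direction.

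**2. Reproducing the plan's 26 per group.** Inputs from the sample size text: means 3.0 and 2.2, SDs 1.15 and 1.10, power 80%, 1:1 allocation.

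- d = (3.0 − 2.2)/√((1.15² + 1.10²)/2) = 0.8/1.125 = 0.711, as stated. This is a one-group before-after change used as a between-group difference, so it assumes no change under HEX.
- Power comes from the noncentral t with 2n − 2 df and noncentrality d√(n/2). At n=26 this is 0.711 × √13 = 2.56.

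| Test at 5%, d=0.711 | n per group for 80% | Power at 26 | Effect detectable with 80% power at 26 |
|---|---|---|---|
| One-sided | 25.2, so 26 | 81% | d=0.70 |
| Two-sided | 32.04, so 33 | 71% | d=0.79 |

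The stated 26 and 80% reproduce one-sided at 5%. This supports reading the missing level as the 5% default. For comparison, Aim 1 (d=1.22, 85% power) needs 13.1, so 14, two-sided, which is the stated figure. One-sided it would need 10.4, so 11.

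**3. The other Aim 2 statement (n=19, d=1.1, 80%).** 1.32/1.2 = 1.1, so the effect size is computed correctly. The power is not: at 19 per group and d=1.1 it is 91% two-sided and 95% one-sided. The effect detectable with 80% power at n=19 is d=0.93 two-sided (0.934 × 1.2 = 1.12 units) or d=0.82 one-sided.

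**4. Power under an analysis of change.** Steps 2 and 3 use an unadjusted t-test. The plan's Aim 2 analysis is a mixed model like that of Aim 1, whose estimand is a difference in change from baseline. With equal variances and baseline-to-follow-up correlation ρ, the SD of a change is SD√(2(1 − ρ)), so the effective d is 0.711/√(2(1 − ρ)). Two-sided 5%, 26 per group:

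| ρ (assumed) | Effective d | Power |
|---|---|---|
| 0.4 | 0.649 | 63% |
| 0.5 | 0.711 | 71% |
| 0.6 | 0.795 | 80% |
| 0.7 | 0.918 | 90% |

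With adjustment for baseline instead, the effective d is 0.711/√(1 − ρ²), and power is 78% to 94% over the same range. The documents state no ρ.

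**The case against.** The best defence is that nothing here breaks the plan's own rules. The default sentence allows exceptions, the Aim 2 paragraph records one in advance, the hypothesis is directional, and the 26 per group fits a one-sided test. That stands: a reader might infer a contradiction, and there is none. What is missing is a reason for the exception.

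Several stronger readings are tempting, and the documents do not support them.

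- **That 80% power exists only because the test is one-sided.** This is true of an unadjusted t-test but not shown for the planned model. Two-sided power by change score reaches 80% at ρ=0.6. The pilot hints at a high correlation: if its p=0.003 came from a two-sided paired t-test on seven people (an assumption), the SD of change is about 0.44 and ρ about 0.92. Seven people in one arm is weak evidence, but 71% cannot be called the power of the planned analysis.
- **That 19 is the number expected to be analysed out of 26.** No dropout rate is given, and the text ties 19 only to Aim 1, where the stated figure is 14.
- **That the two Aim 2 power statements use different sidedness.** The d=1.1 claim fails at n=19 on either basis. It matches a two-sided test only if 14 is substituted for 19, which is conjecture.
- **That a result favouring HEX would be hidden.** The mixed model still gives a signed estimate, and sway, patient-reported outcomes and falls remain under the two-sided default.

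**Conclusion.** The point holds as an unjustified looser standard for one aim. The false-positive rate for Tango benefit on gait is 5% rather than 2.5%, and superiority of the active control cannot be declared significant. This rests on carrying the 5% default into Aim 2, which the reproduction of 26 per group supports.

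The power figures of 81% one-sided and 71% two-sided belong to an unadjusted two-sample t-test with all 26 per group analysed and d=0.711 taken as a between-group effect. Power under the planned model is undetermined without a stated ρ. Separately from sidedness, the n=19 statement is wrong as written.

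Importance is minor to moderate. Sway is the primary endpoint and is tested two-sided, and part of the Aim 2 text is framed as groundwork for future trials.

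**What to change.** 1. In the Aim 2 paragraph of the Statistical Analysis Plan, replace the one-sided test with a two-sided test at 5% (or state one-sided at 2.5%). Report a two-sided 95% confidence interval for the between-group difference in change.
2. In the Aim 2 sample size text, state the sidedness and the method. On an unadjusted two-sample t-test with 26 analysed per group, two-sided power is 71% for d=0.711, and 80% power is reached at d=0.79. For n=19, replace d=1.1 with d=0.93 (two-sided).
3. State the assumed baseline-to-follow-up correlation and give the power of the planned analysis over a range, for example the 63% to 90% for ρ from 0.4 to 0.7 shown above.

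The cost is a wording change with no added participants. The downside is a less favourable stated Aim 2 power on the simple calculation. Under the planned analysis the loss may be small if the correlation is moderate to high.

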Prospective 1:1 block randomized study, with random block sizes. Two arms: experimental and active control (Fig 1).

B. Sample

Individuals with breast cancer-related neuropathy will be recruited for this study using the following inclusion and exclusion criteria.

Inclusion criteria:

- Breast cancer survivors \geq 40 years old
- Symptomatic for neuropathy (CIPN20 sensorimotor score < 95 on transformed scale (100 maximum));
- postural control outside 70% CI for adults who are middle-aged without neurotrauma [20]);
- having completed taxane-based chemotherapy treatment at least 3 months ago;
- able to understand and comply with directions associated with testing and study treatments.

Exclusion criteria:

- Pre-existing vestibular deficit;

[figure not shown]

Fig1: Study design flowchart. TP = Testing timepoint.

- poorly controlled diabetes (hgA1C \geq 8);
- non-ambulatory or lower extremity amputation (assistive devices allowed);
- use of cytotoxic therapy during study (immune- and endocrine therapy allowed);
- participation in physical therapy during the study;
- contraindication to participate in Tango due to orthopedic issue (e.g., herniated vertebral disc);

In addition, survivors who are screened and found eligible to participate in this RCT will be asked to invite a companion to enroll with them in the study arm that the survivor is randomized into. (n=up to 100 companions)

Finally, up to 100 survivors screened who do not meet the criteria above will be offered enrollment without compensation in the intervention of their choice, along with their companion (up to n=100), as we have capacity to include them and using the “companion” consent form. Capacity will be defined based on space and staffing availability.

Therefore, in total, up to 200 survivors and up to 200 companions will be enrolled in Phase 2 of this protocol.

C. Measurement/Instrumentation

Data collected at baseline x 4, mid-intervention and post intervention (*collected at baseline x1 only):

- Adverse events (i.e., PRO-CTCAE[26], falls or loss of balance, illness or hospitalization since last visit)
- SF-36[25]
- EORTC QLQ-C30[15]
- Neuropathy symptoms: measured using original or modified forms of the EORTC CIPN-20[16]
- Sports Concussion Assessment Test (SCAT) Symptom inventory (for comparison to CIPN-20)[27,28]
- Pain: measured using original or modified forms of the Brief Pain Inventory (BPI)[29]

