- Fatigue: measured using original or modified forms of Cancer Related Fatigue (CRF) scales
- Rating of Perceived Exertion (RPE)
- Quantified measures via portable force plate: medial-lateral sway area, range, mean and variability during bilateral static standing with eyes closed[20]
- Timed-Up-and-Go (TUG)[30,31]
- Quantitative gait stability measures via portable motion capture system: average and variability measures of spatiotemporal gait parameters (e.g., stride length, stride time, step width)[22]*
- Mini-BEST[32]*
- Grip strength[33]*
- Goal Attainment Scale (GAS)[34]*
- Activities of Daily Living (ADL) [35] (e.g., Lawton-Brody iADL, Functional Status Questionnaire (FSQ) ADL, Katz ADL, QuickDASH[36])*
- Functional Fitness of Older Adults test [37]*
- Non-invasive Electroencephalography (EEG)*

Data collected within-session (before and after each session unless otherwise noted):

- Adverse events (before every session)
- Neuropathy: measured using original or modified forms of the EORTC CIPN-20[16]

- Sports Concussion Assessment Test (SCAT) Symptom inventory (for comparison to CIPN-20)[27,28]
- Pain: measured using original or modified forms of the Brief Pain Inventory (BPI)[29]
- Fatigue: measured using original or modified forms of Cancer Related Fatigue (CRF) scales
- Rating of Perceived Exertion (RPE)
- Quantified measures via portable force plate: medial-lateral sway area, range, mean and variability during bilateral static standing with eyes closed[20]
- satisfaction with intervention via 7-pt Likert Scale (after every session)[38]
- Goal Attainment Scale (GAS)[34] (before session, no more than once a week)
- Intrinsic Motivation Inventory (IMI)[39] (after session, no more than once a week)

Data collected by participant at home, daily, and reported to research staff on weekly basis:

We will ask participants to track the adverse event of falls or loss of balance using a daily journal that they take home with them or secure electronic data capture interface (e.g., REDCap, MyCap). We will collect these data weekly during the intervention, and for 6 months following the completion of intervention, through weekly check-ins with all participants

D. Detailed Study Procedures

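### The plan promises intent-to-treat but does not secure RMSml testing after a survivor stops training, and its two testing schedules for the Tango arm conflict

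*Combined protocol and SAP*

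**What the plan says.** All references are to Phase 2 (section IV) of the combined protocol and SAP.

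- **Analysis set.** IV.F, Statistical Analysis Plan, states that, unless otherwise noted, "all analyses will be performed on an intent-to-treat basis".
- **Primary estimand.** IV.F, Aim 1, targets "the difference in mean RMSml change from baseline to week 16 between treatment groups". It does not say how stopping training is handled.
- **RMSml schedule in the primary-measure text.** IV.D, Aim 1, item a, sets twice-weekly tests during baseline, then "monthly thereafter for HEX, and before and after each session for the Tango group".
- **Common schedule.** IV.C opens its first list with "Data collected at baseline x 4, mid-intervention and post intervention (*collected at baseline x1 only". That list includes "medial-lateral sway area, range, mean and variability during bilateral static standing with eyes closed[20", without the asterisk and without a split by arm. Readings taken before and after sessions form a separate list.
- **Attrition.** IV.F says "Not all enrolled subjects will complete the intervention and have follow-up data". It adds that the mixed model "can use available data from all participants with at least one observation, regardless of whether or not they complete follow-up", and plans a baseline comparison of completers with drop-outs and a multiple-imputation sensitivity analysis.

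**The concern.** An intent-to-treat contrast needs the week-16 RMSml of everyone randomised, including those who stopped training. The plan names the analysis but does not commit to collecting those data. The attrition sentence runs two events together, ceasing the intervention and having no follow-up, and nothing in the readable text separates them.

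The IV.D schedule makes this matter more in one arm. A HEX survivor who stops exercising still has a monthly test date. A Tango survivor who stops attending has no session, and under that text no test. Missing RMSml in Tango would then be driven by attendance, and attendance may be related to response, fatigue or falls.

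The planned methods do not repair this. Mixed models of observed data usually rest on missing at random, as does multiple imputation in its standard form, and IV.F states no other assumption. Comparing baseline characteristics cannot show divergence after baseline. Readings that were never taken cannot be recovered at analysis.

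**Working it through.** **1. The plan's own figure.** From IV.F, Sample Size Justification, Aim 1: pilot RMSml fell from 7.9 to 4.6 mm, so the effect is 7.9 − 4.6 = 3.3 mm. With SD 2.7, d = 3.3/2.7 = 1.22. A two-sample t-test (two-sided 5%, 85% power) needs 13.1 per group, which rounds up to the stated 14. Power at 14 is 87.4%. The sample-size arithmetic reproduces and is not in dispute.

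**2. The schedules side by side.**

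| Source | HEX | Tango | Tied to class attendance? |
|---|---|---|---|
| IV.D, Aim 1, item a | monthly | before and after each session | Tango only |
| IV.C, first list | mid- and post-intervention | mid- and post-intervention | neither arm |

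Both cover the primary measure, and they differ for Tango. The common tests are named relative to the intervention. No date is given for someone who has stopped.

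**3. The endpoint date.** IV.D, Aim 1, item b, places adverse-event recording before Tango lessons twice a week. Sixteen sessions at that rate take 16/2 = 8 weeks, but the estimand is at week 16. Under session-based testing, even a full attender would have no class reading then. These passages must also be reconciled.

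**4. Illustrative size.** Let p be the share of Tango survivors who stop and have no later RMSml, and r the share of the 3.3 mm benefit they keep. Suppose the model treats them like attenders and so returns 3.3 mm.

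- All-randomised difference = 3.3 × [1 − p(1 − r)]
- Overstatement = 3.3 / (all-randomised difference) − 1

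Both p and r are assumptions, since the documents give no drop-out rate. The 27% is 1 − 19/26, from the 19 per group in the Aim 2 power statement and the 26 enrolled. It is a reference value, not a stated allowance.

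| p | r | All-randomised difference | Overstatement | Power, 26 per group tested |
|---|---|---|---|---|
| 10% | 0 | 3.3 × 0.900 = 2.97 mm | 0.33 mm (11%) | 97% |
| 20% | 0 | 3.3 × 0.800 = 2.64 mm | 0.66 mm (25%) | 93% |
| 27% | 0 | 3.3 × 0.731 = 2.41 mm | 0.89 mm (37%) | 88.5% |
| 27% | 0.5 | 3.3 × 0.865 = 2.86 mm | 0.44 mm (16%) | 96% |

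The last column uses the same t-test with SD 2.7 and all 26 per group tested. These are simple end-point contrasts, not a fit of the planned mixed model.

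**The case against.** The strongest reply is that IV.C already provides tests for both arms that do not depend on attendance, and that IV.D, Aim 1, item c, gives the session readings their own purpose: within-session change. On that reading a Tango stopper can still be tested. This stands in part. It shows that the documents conflict, not that they plainly leave stoppers untested. It does not supply the missing rule or a test date for someone who has stopped.

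Second, the mixed model conditions on each survivor's own earlier readings, and frequent session tests give a Tango stopper more of them. This stands too: bias arises only if missingness still depends on unobserved outcomes, and its direction depends on stoppers doing worse.

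Three stronger readings are tempting, and the documents do not support them.

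- *The contrast becomes Tango attenders against everyone in HEX.* The attrition sentence covers both arms, HEX survivors can also miss monthly tests, and Tango stoppers' earlier readings stay in the model.
- *The plan expects stoppers to have no follow-up.* The sentence admits attrition. It does not say that stoppers go untested.
- *The plan allows for 46% missing endpoints (12 of 26), hence an 86% overstatement.* Fourteen is the number required for power, and 26 was set for drop-out and Aim 2 together, so 14/26 is not a drop-out allowance.

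Finally, the design flowchart that marks the testing timepoints could not be read, and consent pages were not available. A rule could appear there. If so, it should be repeated in IV.D and IV.F.

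**Conclusion.** The concern holds in conditional form. No readable passage secures RMSml testing after training stops, and the primary-measure schedule conflicts with the common visits. If the primary-measure schedule is followed as written, missingness in Tango depends on attendance, and the promised intent-to-treat contrast may lean towards attenders.

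The overstatement of 11% to 37% is an illustration. It requires that stoppers are unobserved, keep no benefit, and are modelled like attenders, at stopping rates of 10% to 27%. Keeping half the benefit brings the 27% case down to 16%. Full loss of benefit may be pessimistic, because the pilot gain of 3.3 mm was reached after 8 sessions, half the planned 16. Neither the rate of stopping nor the direction of bias can be established from the documents. The change is worth making because it is cheap and the data cannot be recovered later.

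**What to change.** 1. Reconcile the RMSml schedule in IV.D, Aim 1, item a, with the common list in IV.C, and both with the week-16 estimand and the session frequency. The result should be the same RMSml tests in both arms, on dates fixed from randomisation.
2. Add to IV.D and IV.F wording such as: *Stopping training is not withdrawal from the study. Every randomised survivor in either arm is invited to the common RMSml tests on their fixed dates, whether or not training continues.*
3. Base the primary contrast on those common tests, including readings taken after training stopped. Keep the session readings for the within-session analysis.
4. Report by arm how many stopped training and how many of those were tested.

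**Cost.** Protocol wording and a few test visits for survivors who stop, most of them already listed in IV.C. The estimate may be less favourable to Tango. Power looks affordable: with all 26 per group tested, 27% stopping and no retained benefit, it is 88.5%, above the planned 85%.

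### The only drop-out sensitivity analysis is unspecified multiple imputation with no not-at-random scenario; in its usual form it would largely reproduce the mixed model

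*Combined protocol and SAP*

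**What the plan says.** All of this is in section IV.F (Data Analysis).

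- The Statistical Analysis Plan accepts that outcomes will be missing: "Not all enrolled subjects will complete the intervention and have follow-up data".
- The primary handling is by likelihood: "The linear mixed model analyses can use available data from all participants with at least one observation". The target is "the difference in mean RMSml change from baseline to week 16 between treatment groups".
- One descriptive check is planned: "We will compare the baseline characteristics of subjects who complete the study to those who drop out to assess the potential for attrition bias".
- One sensitivity analysis is planned: "A sensitivity analysis will be performed using multiple imputation to assess the impact drop-out has on study conclusions".

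The text stops there. It gives no imputation model, list of predictors or missingness assumption, and it mentions no delta-adjusted, reference-based, pattern-mixture or tipping-point analysis. The Sample Size Justification raises enrolment to 26 per group "To account for anticipated drop-out and Aim2 analysis" but gives no drop-out rate.

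**The concern.** A sensitivity analysis for drop-out is useful only if it relaxes the assumption that the primary analysis makes about unseen outcomes. A likelihood mixed model assumes that, given the data in the model, those who leave would have followed the same course as similar participants who stay. Multiple imputation in its usual form assumes the same thing. Agreement between the two would then be reported as reassurance without having tested anything.

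Informative drop-out is plausible here. Participants who feel no benefit, or whose balance worsens, may leave a movement programme. Section IV.B excludes physical therapy and cytotoxic therapy during the study, and these are treatments that someone who is deteriorating might need. Section IV.D measures posture around every session in Tango but monthly in HEX, so burden, and perhaps drop-out, may differ by arm. At stake is a claim of benefit over HEX that may partly reflect who stayed.

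**Working it through.** **1. The plan's own figure.** Section IV.F gives RMSml falling from 7.9 to 4.6 mm and an assumed SD of 2.7. So d = (7.9 − 4.6)/2.7 = 3.3/2.7 = 1.22. At two-sided 5% and 85% power, the normal approximation gives 13 per group. The noncentral t gives 13.10, rounded up to 14, where power is 87.4%. The stated 14 reproduces and is not in dispute. It supplies the scale used below: 3.3 mm and SD 2.7.

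**2. Amount of missing data.** None is stated. Two illustrative rates per arm were used: 7/26 = 27% (as if 19 of 26 remained) and 12/26 = 46% (as if 14 remained). Both are assumptions.

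**3. Do the two methods differ under informative drop-out?** Setup: 26 per arm and 300 simulated trials per scenario. Assumptions not in the documents: four equally spaced visits, SD 2.7 at each, correlation 0.5, and drop-outs losing the last two visits. Tango drop-outs are mostly those with poor unseen final sway; HEX drop-outs are random. Three estimates of the Tango-minus-HEX change were compared (negative favours Tango):

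- full data, with nothing missing;
- a likelihood repeated-measures model with unstructured covariance, standing in for the planned mixed model;
- missing-at-random imputation on arm and earlier RMSml.

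| Missing | True effect (mm) | Full data | Model | Imputation | Model − full data |
|---|---|---|---|---|---|
| 27% | 0 | 0.01 | −0.54 | −0.55 | −0.55 |
| 27% | −1.5 | −1.57 | −2.11 | −2.10 | −0.54 |
| 27% | −3.3 | −3.31 | −3.92 | −3.91 | −0.61 |
| 46% | 0 | 0.02 | −0.91 | −0.90 | −0.93 |
| 46% | −1.5 | −1.54 | −2.48 | −2.47 | −0.94 |
| 46% | −3.3 | −3.30 | −4.19 | −4.19 | −0.89 |

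Within a trial, the model and imputation estimates correlated at 0.993 to 0.997. Their difference had an SD of 0.07 to 0.12 mm, against a standard error of about 0.84 to 1.00 mm. The bias could not be seen by comparing them.

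**4. Would a not-at-random analysis be informative?** Adding delta (worse sway) to imputed final Tango values moves the contrast by about (share of Tango missing) × delta. The delta that brings the estimate to zero is therefore effect ÷ share missing:

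| Missing | 1.5 mm effect | 2.0 mm effect | 3.3 mm effect |
|---|---|---|---|
| 27% | 5.6 | 7.4 | 12.3 |
| 46% | 3.2 | 4.3 | 7.2 |

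Significance goes sooner. With random drop-out in both arms, delta applied to Tango only and 150 trials per cell, the rejection rates were:

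- True effect 2.0 mm, 27% missing: 68% at delta 0, 56% at 1 mm, 33% at 2 mm, 28% at 3.3 mm.
- True effect 2.0 mm, 46% missing: 53% at delta 0, 31% at 1 mm, 17% at 2 mm.
- True effect 3.3 mm, 27% missing: 99% at delta 0, 79% at 3.3 mm, 51% at 5 mm.

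The last line shows why the range should not stop at 3.3 mm: in 79% of those trials the tipping point had not been reached there.

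**5. The completer comparison.** It uses baseline data only. Two groups can match at baseline and differ in unseen week-16 sway, so it cannot detect drop-out that depends on unseen outcomes.

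**The case against.** The strongest reply is that the text says only multiple imputation. A reader might infer that the sponsor has chosen the missing-at-random form and that it must repeat the primary result. The documents support neither step. The method is unspecified and could have been meant as delta-adjusted or reference-based. Even under missing at random, the trial collects diaries of falls and symptoms, satisfaction and motivation scores (sections IV.C and IV.D). Imputation using these would rest on a weaker assumption than the mixed model and could give a different answer. The near-identity shown above comes from imputing on arm and earlier RMSml alone. The dense Tango posture data might also let the planned model pick up worsening before drop-out and so reduce the bias.

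A reader might also take enrolling 26 for an analysis sample of 14 as an expected 46% loss. It is not: the 26 also serves Aim 2, which justifies it separately, and nothing says that 19 or 14 of 26 will remain.

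Finally, one might argue that if benefit disappears in everyone who leaves, a 3.3 mm effect becomes 3.3 × 19/26 = 2.41 mm, so the estimate is 26/19 − 1 = 37% too large. That only restates the no-benefit assumption. Likewise, reference-based imputation would recover the smaller figure because it makes the same assumption.

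These points stand, and they limit the claim. They do not supply a not-at-random analysis or say what the imputation will be.

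**Conclusion.** The concern holds in conditional form. What the documents show is an unspecified imputation and no committed departure from missing at random. This is more than missing detail, because the named method in its usual form cannot do the job that the plan gives it. The agreement of the two missing-at-random methods did not vary across the scenarios run. The bias of about 0.5 to 0.9 mm is illustrative: it depends on the assumed drop-out share, mechanism, visit pattern and correlation, and is not a forecast for this trial. If a not-at-random method was intended, the plan still needs to say so. The change should be made before outcomes are seen, so that scenarios cannot be chosen to suit the result.

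**What to change.** Keep the mixed model as primary and replace the sensitivity sentence with:

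> Multiple imputation will use arm, all earlier outcome values and post-baseline auxiliary data (attendance, symptoms, falls). Sensitivity to informative drop-out will be assessed by (a) reference-based imputation, with missing Tango outcomes imputed from the HEX trajectory, and (b) delta-adjusted imputation, varying delta separately by arm in 0.5 mm steps for RMSml until the primary conclusion changes, and reporting that tipping point. The same approach, with steps on the CVspeed scale, will be used for Aim 2.

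Because per-session posture exists only in Tango, the plan should also say that the reference-based step uses the visits common to both arms.

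The cost is SAP wording and modest extra programming, with no new data. The sensitivity result may look less favourable than the primary one.
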